### 7.2 Study Conduct

All randomized patients are included in the analysis of study conduct. Information will be tabulated by randomized treatment (unless otherwise indicated) and pooled treatments.

#### 7.2.1 Patient Disposition and Follow-up

- Number of patients randomized (**Table 1**)

- Number of patients on RT+BSC received and not received RT (**Table 1**)
- Reasons of patients on RT+BSC not received RT (**Table 1**)
- Number of patients on BSC received and not received RT after their day 30 assessment (**Table 1**)
- Reasons of patients on BSC not received RT after their day 30 assessment (**Table 1**)
- Number of alive patients (**Table 2**)
- Median (estimated by Kaplan-Meier method) and range (minimum and maximum) (**Table 2**) of the follow-up time (months) defined as time from the day of randomization (as recorded in centralized randomization file) to the last day the patient is known alive (LKA) as the last recorded date known alive or censored at the time of death and calculated as

$$[(\text{date of death or LKA} - \text{date of randomization}) + 1]/30.4375.$$

### 7.2.2 Accrual Patterns

- Number of patients accrued by center (**Table 3**)
- Number of patients by stratification factor (except center) at randomization (**Table 4**)
- Accrual of patients by calendar time (**Figure 1**)

### 7.2.3 Eligibility Violations/Protocol Deviations

Eligibility violations of inclusion or exclusion criteria are centrally reviewed by CCTG; a field (y/n) for eligibility status and reason for ineligibility is entered in the database. A major protocol violation (MPV) is defined as a deviation from the protocol, initiated by the center or the investigator, serious enough to mean that the patient's data contributes little, if any, information on the efficacy or toxicity of the regimen under study. MPVs are coded by CCTG based on its standard codes.

- Number of patients eligible, not eligible (**Table 5**)
- Reasons for ineligibility (**Table 5**)
- Major protocol violations: % for each type of violations (**Table 5**)

## 7.3 Study Population

All randomized patients are included in the study population analyses.

### 7.3.1 Patient Pretreatment Characteristics

- Gender: male, female (**Table 6**)
- Age: median, minimum, maximum values; number <65,  $\geq 65$  (**Table 6**)
- ECOG Performance Status: 0, 1, 2, 3, 4 (**Table 6**)
- BMI: median, minimum, maximum values (**Table 6**)

### 7.3.2 Patient Baseline Tumour Characteristics

- Months from initial diagnosis to randomization: median, minimum, maximum values (**Table 7**)
- Method of initial diagnosis (**Table 7**)
- Type of liver cancer (**Table 7**)

- Months from liver metastases diagnosis to randomization: median, minimum, maximum values (**Table 7**)
- Primary tumour type of liver metastases (**Table 7**)
- Presence of extrahepatic cancer (**Table 7**)
- Primary in place for extrahepatic cancer (**Table 7**)
- Sites of metastases (**Table 7**)
- Portal vein or other vascular invasion (**Table 7**)
- Type of other liver disease (**Table 7**)
- Extent of liver disease (**Table 7**)
- Child-Pugh class (**Table 7**)
- Child-Pugh score (**Table 7**)

### 7.3.3 Prior Cancer Therapy

- Number of patients with prior surgical/diagnostic procedures (**Table 8**)
- Procedure/site of prior surgery (**Table 8**)
- Number of patients with prior radiotherapy (**Table 9**)
- Prior radiotherapy by site with duration and total dose (cGy) (**Table 9**)
- Number of patients with prior systemic therapy (**Table 10**)
- Prior systemic therapy by drug or agent name (**Table 10**)
- Number of patients with regional therapy (**Table 11**)
- Prior regional therapy by therapy name (**Table 11**)

### 7.3.4 Baseline Exams

- Baseline grade 2 and higher adverse events (**Table 12**)
- Baseline hematology: hemoglobin, absolute neutrophil count, platelets (**Table 13**)
- Baseline biochemistry: total bilirubin, alkaline phosphatase, ALT, AST, albumin, serum creatinine, alpha-fetoprotein (**Table 14**)
- Baseline coagulation (**Table 15**)

### 7.3.5 Concomitant Medications at Baseline

- Number of patients with concomitant medication within 14 days prior to the date of randomization (**Table 16**)

## 7.4 Extent of Radiotherapy

Within 5 working days after randomization, the patients randomized to RT+BSC are planned to receive a single fraction of 8 Gy radiation therapy to the liver. The same radiation therapy may be given to the patients randomized to BSC who continue to be bothered by pain/discomfort following completion of the day 30 assessment. The following information will be summarized for patients who have received the radiotherapy:

- The number of fractions, plan dose, type of motion management, beam arrangement, planning, and position verification (**Table 17**).
- Liver volumes, GTV, CTV, PTV (**Table 18**)
- Doses (**Table 19**).

## 7.5 **Efficacy**

### 7.5.1 **Patient-reported pain/discomfort symptoms**

Patient-reported pain/discomfort symptoms in this study are assessed at baseline, and on days 30 and 90 from randomization by using BPI, which consists of 4 pain intensity and 7 pain interference 11- point Likert-scale questions (range 0-10). The following information on pain/discomfort assessment will be summarized:

- Number of patients who have completed the BPI pain/discomfort assessment at respectively baseline and days 30 and 90 (**Table 20**).
- Reasons the assessments are not completed (**Table 20**).
- Mean and standard deviation of BPI scores at baseline and days 30 and 90 (**Table 21**)

### 7.5.2 **Proportion of patients who experience a significant improvement in symptoms**

The primary endpoint of the study, the proportion of patients who experience significant improvement in symptoms from baseline to day 30, is estimated by the number of patients with  $\geq 2$  point reduction in ‘worst’ pain score on BPI from baseline to day 30 among all primary BPI response evaluable patients. A stratified Cochran-Mantel-Haenszel (CMH) test adjusting for the stratification factor (HCC versus liver metastases) will be used to compare this endpoint between two treatment arms (**Table 22**). A subgroup analysis will be performed based on the location of the metastases (HCC versus liver) (**Table 22**).

As a sensitivity analysis, this primary endpoint will also be estimated among all randomized patients by including those without assessment at day 30 after randomization in the ‘no improvement’ group (**Table 22**).

The proportion of patients who experience significant improvement in symptoms from baseline to day 90, a secondary endpoint of the study, is estimated by the number of patients with a  $\geq 2$  point reduction in ‘worst’ pain score on BPI from baseline to day 90 among all secondary BPI response evaluable patients and analyzed similarly as the primary endpoint (**Table 22**).

For patients who have randomized to BSC arm and crossed over to RT+BSC arm after their day 30 assessment, the proportion of patients who experience significant improvement in symptoms from day to day 90, another secondary endpoint of the study, is estimated by the number of patients with a  $\geq 2$  point reduction in ‘worst’ pain score on BPI from day 30 to day 90 among all BPI response from day 30 to day 90 evaluable patients (**Table 22**).

### 7.5.3 **Proportion of patients achieving improvement in other BPI pain scores**

For all other BPI scores, the proportions of patients who had a  $\geq 2$  point reduction in from baseline to days 30 and 90 will be calculated among respectively all primary and secondary BPI response evaluable patients and analyzed similarly as the primary endpoint (**Table 23**).

#### 7.5.4 Opioid Intake

Number of patients using the opioid or non-opioid medications and the type and number of these medications as reported at baseline and 30 and 90 day follow-up visits are summarized in **Table 24**. Oral morphine equivalents (OME) calculated for all opioid medications are also summarized.

The proportion of patients who had achieved 25% reduction in opioid use at 30 days (employing daily morphine equivalence scale) will be compared between two treatment arms using a stratified CMH test adjusting for the stratification factor (HCC versus liver metastases) (**Table 25**). In addition, the proportion of patients who improved liver cancer pain/discomfort by  $\geq 2$  points in pain ‘intensity at worst’ AND with no increase in opioid use (employing daily morphine equivalence scale) from baseline to 30 days will also be compared between two treatment arms using a stratified CMH test adjusting for the stratification factor (HCC versus liver metastases) (**Table 26**).

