8.1 Best Supportive Care (Arms 1 and 2)

Patients on both treatment arms will receive BSC, with analgesia as needed and palliative care/pain specialist involvement in their care (per local policy). The treating team will determine the most appropriate interventions for individual patients. In general, analgesia strategies that may be considered include:

- Opioids: Short-acting hydromorphone q 2-4 hours prn is the opioid of choice with the dose individualized and titrated to maximize pain relief effect and minimize side effects. A longer interval between dosing may be needed for patients with more impaired liver function. Long acting hydromorphone may also be used if around-the-clock pain relief is required. The pharmacokinetics of fentanyl and methadone are not significantly affected by hepatic impairment, so they are alternatives in the setting of liver failure [Smith 2009]. Other opioids are also permitted;
- Steroids: Dexamethasone is sometimes useful in these patients. If patients are on dexamethasone, it is recommended that they stay on the same dose for at least 3 days before entering the trial with no plans for altering the dose during the first month of the study, if clinically suitable. Note that even if patients are taking regular steroids, anti-emetics one hour prior to RT delivery, including a steroid, should be delivered (see section 8.3.1); and,
- Acetaminophen: 325 mg to 1 g q 4 hours, up to 3 g per day.

It is recommended that patients bring their pain medication pill bottles to each follow-up appointment and that the study nurse or CRA review the medication table completed by the patient (in Part Two of the Pain/Discomfort and Medication Questionnaire). All changes in pain medication, including steroid and over the counter analgesia, should be recorded.

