10.0 CRITERIA FOR MEASUREMENT OF STUDY ENDPOINTS

10.1 Definitions

10.1.1 Evaluable for adverse events. All patients will be evaluable for adverse event evaluation from the time of randomization.

10.1.2 Evaluable for BPI response. All patients who have completed a baseline and 30 days follow-up BPI will be considered evaluable for the primary endpoint. Patients who complete a baseline and a day 90 follow-up BPI will be considered evaluable for secondary BPI endpoints. Patients from Arm 1 who cross over to Arm 2 after their day 30 assessment are evaluable for BPI response from day 30 to day 90, if they have completed their day 30 and day 90 BPI.

10.1.3 Evaluable for quality of life assessment. All patients who have completed the quality of life questionnaire at baseline and on days 30 and 90 are evaluable for the quality of life endpoint.

10.1.4 Evaluable for change in opioid analysis. All patients who have completed Pain/Discomfort and Medication Questionnaires at baseline and within 24 hours of the 30 day visit are eligible for assessment. Only analgesic use in the past 24 hours will be recorded to increase compliance. If the patient is too unwell to visit the clinic, the Pain/Discomfort and Medication Questionnaire can be completed by the study nurse following a telephone call to the patient. Note: large fluctuations in opioid use are unlikely to occur due to intolerability of medications for many patients.

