### **6. Data Set Descriptions**

Two types of analysis samples will be used:

All Randomized Patients:

All patients who have been randomized in the study with the treatment arm being as randomized.

All Treated Patients:

All patients who are randomized to RT+BSC arm and have received a single 8 Gy dose of RT and all patients who are randomized to BSC arm.

All Day 30 BPI Response Evaluable Patients:

All patients who have completed a baseline and 30 days follow-up BPI.

All Day 90 BPI Response Evaluable Patients:

All patients who have completed a baseline and a day 90 follow-up BPI.

All BPI Response from Day 30 to Day 90 Evaluable Patients:

All patients who have randomized to BSC arm and crossed over to RT+BSC arm after their day 30 assessment and also completed their day 30 and day 90 BPI.

All QoL (quality of life) Evaluable Patients:

All patients who have completed the quality of life questionnaire at baseline and on days 30 and 90.

All Change in Opioid Evaluable Patients:

All patients who have completed Pain/Discomfort and Medication Questionnaires at baseline and within 24 hours of the 30 day visit.

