**Table 24: Opioid and Non-Opioid Intake**

Data set: All Randomized Patients						
	Baseline		Day 30		Day 90	
	RT+BSC	BSC	RT+BSC	BSC	RT+BSC	BSC
Any Opioid Medication Intake						
No	** (**)	** (**)	** (**)	** (**)	** (**)	** (**)
Yes	** (**)	** (**)	** (**)	** (**)	** (**)	** (**)
Generic Opioid Name 						
Opioid #1	** (**)	** (**)	** (**)	** (**)	** (**)	** (**)
Opioid #2	** (**)	** (**)	** (**)	** (**)	** (**)	** (**)
Opioid #3	** (**)	** (**)	** (**)	** (**)	** (**)	** (**)
...	** (**)	** (**)	** (**)	** (**)	** (**)	** (**)
Number of Opioid Taken 						
N	**	**	**	**	**	**
Median	**	**	**	**	**	**
Min - Max	** **	** **	** **	** **	** **	** **
—	—	—	—	—	—	—
Oral morphine equivalents						
N	**	**	**	**	**	**
Median	**	**	**	**	**	**
Min - Max	** **	** **	** **	** **	** **	** **
—	—	—	—	—	—	—
Any Non-Opioid Medication Intake						
No	** (**)	** (**)	** (**)	** (**)	** (**)	** (**)
Yes	** (**)	** (**)	** (**)	** (**)	** (**)	** (**)
Generic Non-Opioid Name 						
Opioid #1	** (**)	** (**)	** (**)	** (**)	** (**)	** (**)
Opioid #2	** (**)	** (**)	** (**)	** (**)	** (**)	** (**)
Opioid #3	** (**)	** (**)	** (**)	** (**)	** (**)	** (**)
...	** (**)	** (**)	** (**)	** (**)	** (**)	** (**)
Number of Non-Opioid Taken 						
N	**	**	**	**	**	**
Median	**	**	**	**	**	**
Min - Max	** **	** **	** **	** **	** **	** **
—	—	—	—	—	—	—

 Patient may have more than one opioid or non-opioid medications.

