**Table 25: Proportion of Patients with Reduction in Opioid Use at Day 30**

Patients who have completed Pain/Discomfort and Medication Questionnaires at baseline and day 30	RT+BSC N (%)	BSC N (%)	CMH P-value 
Patients with 25% Reduction in Opioid Use 	** (**.**)	** (**.**)	0.***

 Stratified Cochran-Mantel-Haenszel test adjusting for the stratification factor (HCC versus liver metastases) 25% Reduction in opioid use from baseline to day 30 (employing daily morphine equivalence scale).**Table 26: Proportion of Patients with Improved BPI and no Increasing Opioid Use at Day 30**

Patients who have completed Pain/Discomfort and Medication Questionnaires at baseline and day 30	RT+BSC N (%)	BSC N (%)	CMH P-value (*)
Patients with Improved BPI and no Increasing Opioid Use	** (**.**)	** (**.**)	0.***

\* Stratified Cochran-Mantel-Haenszel test adjusting for the stratification factor (HCC versus liver metastases)

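### The 25% opioid-reduction endpoint is computed in all questionnaire completers, including patients on no opioid at baseline, for whom it cannot be met or is undefined

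*SAP*

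**What the plan says.** The opioid endpoint is a listed secondary endpoint (SAP 4.2) with a planned stratified CMH p-value in Table 25. SAP 7.5.4 describes it as "The proportion of patients who had achieved 25% reduction in opioid use at 30 days", measured on a daily morphine-equivalence scale. The Table 25 footnote defines it as "25% Reduction in opioid use from baseline to day 30".

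Three places fix the denominator, and they agree:
- SAP section 6, opioid-evaluable set: "All patients who have completed Pain/Discomfort and Medication Questionnaires at baseline and within 24 hours of the 30 day visit".
- Protocol 10.1.4, in the same terms and with the same visit as reference: "Evaluable for change in opioid analysis. All patients who have completed Pain/Discomfort and Medication Questionnaires at baseline and within 24 hours of the 30 day".
- Table 25 row header: "Patients who have completed Pain/Discomfort and Medication Questionnaires at baseline and day 30".

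None of them requires opioid use at baseline, and none says how to classify a patient whose baseline OME is 0.

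The plan does foresee such patients. No criterion in protocol 5.1 or 5.2 requires opioid use. Protocol 8.1 introduces opioids, steroids and acetaminophen with "In general, analgesia strategies that may be considered include", so opioids are one option among several. SAP Table 24 has No and Yes rows under "Any Opioid Medication Intake" at baseline.

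**The concern.** A percentage reduction needs a non-zero starting value. For a patient on no opioid at baseline and none at day 30, percent change is 0/0. The denominator includes this patient, but the endpoint definition does not cover the case.

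Three codings are compatible with the text. Requiring an actual reduction makes the patient a permanent non-responder. Testing whether day-30 OME is at most 0.75 times baseline makes the patient a success, because 0 is not greater than 0. Calculating percent change directly returns a missing value and removes the patient without any stated rule. The published rate, and to some extent the p-value, would then rest on a programming choice. This SAP was written after accrual had closed in an open-label trial (SAP 2.3), so the rule should be on paper before the table is produced.

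The plain reading also has a cost: patients who cannot respond pull both arms' rates towards zero and narrow the difference between them.

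**Working it through.** **Plan's own figures.** Neither document gives a sample size or power for the opioid endpoint. For the primary endpoint, SAP section 5 gives 45 evaluable patients for 5% v 40%, 80% power, two-sided 0.05. The pooled normal formula for two proportions gives 22 per arm, 44 in total, which is close to 45. For 42 patients the SAP states 77% power. The pooled formula gives 79.7% and exact Fisher 74.5%, so 77% is not reproduced exactly. The powers below are for comparing options, not for quoting as precise values.

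**Inputs.**
- 21 per arm: 42 evaluable patients (SAP 2.3) split 1:1. The 42 is the count for the primary endpoint; using it for the opioid set is an assumption.
- Response among baseline users of 5% (BSC) v 40% (RT+BSC): borrowed from the primary endpoint. This is an assumption.
- Share of non-users f: not in the documents. A range of 10% to 30% is used, the same in both arms.

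**Formulas.** With p the response rate among users:
- (a) Non-users as failures: observed rate = p(1 − f).
- (b) Non-users as successes: observed rate = p(1 − f) + f.
- (c) Users only: observed rate = p, with 21(1 − f) patients per arm.
- Under (a) and (b) alike, observed difference = 35(1 − f) points.
- Power = Φ{[d − 1.96√(2p̄(1 − p̄)/n)] / √([p₁(1 − p₁) + p₂(1 − p₂)]/n)}, where p₁ and p₂ are the two observed rates, d is their difference, p̄ is their mean and n is the number per arm.

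**Worked case, f = 30%, coding (a).** Rates are 0.05 × 0.7 = 3.5% and 0.40 × 0.7 = 28%, so d = 0.245. The null term is 1.96 × √(2 × 0.1575 × 0.8425/21) = 0.2203, and the standard error under the alternative is 0.1059. Power = Φ[(0.245 − 0.2203)/0.1059] = Φ(0.233) = 59%.

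| f | (a) BSC v RT+BSC | (a) power | (b) BSC v RT+BSC | (b) power | Difference, (a) and (b) | (c) power, difference 35 points |
|---|---|---|---|---|---|---|
| 0% | 5% v 40% | 80% | 5% v 40% | 80% | 35 | 80% |
| 10% | 4.5% v 36% | 74% | 14.5% v 46% | 61% | 31.5 | 75% |
| 20% | 4% v 32% | 67% | 24% v 52% | 46% | 28 | 70% |
| 30% | 3.5% v 28% | 59% | 33.5% v 58% | 35% | 24.5 | 63% |

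With equal shares of non-users, the two codings give the same difference but very different rates and power. Restriction keeps the difference at 35 points whatever f is.

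**When the arms differ in non-users.** Suppose there is no treatment effect: 25% response among users in both arms, with 20% non-users in one arm and 40% in the other. Coding (a) gives 0.25 × 0.8 = 20% v 0.25 × 0.6 = 15%. Coding (b) gives 20% + 20% = 40% v 15% + 40% = 55%. The sign of the apparent effect depends on the unstated rule. In users only, it is 25% v 25%.

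**The case against.** The strongest reply is that the plan is adequate on its plain reading. A patient who goes from 0 to 0 has not achieved a reduction, so is a non-responder, and only a clarifying sentence is missing. That reading is the natural one, and coding (b) is strained. But it still leaves in the denominator patients who cannot respond, and the difference narrows in proportion to their share.

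Second, restriction gains little power over the plain reading: 75% v 74% at 10% non-users and 63% v 59% at 30%. This stands, so power is not the main reason for the change.

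Third, the all-completer set is written into protocol 10.1.4, and replacing it after accrual has closed is a departure. This also stands, and is why that set should stay in the table as a supplementary row.

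Three stronger readings are tempting and are not supported:
- **That the endpoint no longer measures opioid sparing.** It does, in diluted form; users still drive the difference between arms.
- **That imbalance in non-users biases the comparison.** Randomization balances them in expectation. If each arm of 21 is binomial, the chance that the arms differ by three or more non-users is 7%, 19%, 33% and 40% for shares of 5%, 10%, 20% and 30%. That is the probability of a count difference, not a bias. Under the plain reading, three extra non-users move an arm's rate by 3/21 × 15% = 2 points to 3/21 × 40% = 6 points for user response of 15% to 40%. Table 24 would show any imbalance.
- **That the 2-point rule for the other BPI items in Table 23 has the same fault.** An item scored 0 or 1 at baseline cannot fall by 2, but the outcome is defined for every patient and not improved is a valid class. A baseline minimum of 2 would also not fit the day 30 to 90 column or the percentage-relief row.

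**Conclusion.** The concern holds for Table 25. The stated denominator includes patients who cannot meet the endpoint, or who meet it automatically under one coding, and the plan does not say which applies. Under the assumptions above (10-30% non-users, equal between arms; 21 per arm; 5% v 40% among users), the difference falls from 35 points to 31.5-24.5 points. Power is 74-59% with non-users as failures or 61-35% with non-users as successes, against 75-63% in users only. The size depends on the share of non-users and on the user response rates, neither of which the documents give.

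The scope is one secondary endpoint. The primary endpoint is untouched, since worst pain must be at least 4 at baseline. The Table 26 composite is well defined for non-users, because no increase from 0 can be assessed.

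**What to change.** In SAP section 6, SAP 7.5.4 and Table 25:
1. Make the main analysis set the questionnaire completers with baseline OME above 0.
2. Define success as day-30 OME at or below 75% of baseline.
3. Report by arm, separately, the number on no opioid at baseline and how many of them had started one by day 30.
4. Keep the protocol's all-completer set as a supplementary row, with zero-baseline patients counted as non-responders.
5. Leave Tables 23 and 26 as they are on this point.

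The restriction uses pre-randomization data, so it does not itself introduce selection after randomization. The set still depends on completing the day-30 questionnaire, as it does now.

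The cost is a few lines of SAP text, a smaller denominator (about 19 per arm at 10% non-users and 15 at 30%, from 21), and a documented departure from the protocol 10.1.4 set. The gain is a rate with a clear meaning that does not depend on how a zero baseline is programmed.
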